#### 7.2.2 IRB Requirements for PI Reporting at Continuing Review

Please refer to the reporting requirements in Policy 801: Reporting Research Events found at: <https://irbo.nih.gov/confluence/pages/viewpage.action?pageId=36241835#Policies&Guidance-800Series-ComplianceandResearchEventReportingRequirements>.

### **7.3 NCI CLINICAL DIRECTOR REPORTING**

Problems expeditiously reviewed by the OHSRP in the NIH eIRB system will also be reported to the NCI Clinical Director/designee; therefore, a separate submission for these reports is not necessary.

In addition to those reports, all deaths that occur within 30 days after receiving a research intervention should be reported via email unless they are due to progressive disease.

To report these deaths, please send an email describing the circumstances of the death to the Clinical Director/designee at [[contact]](mailto:[contact]) within one business day of learning of the death.

### **7.4 NIH REQUIRED DATA AND SAFETY MONITORING PLAN**

#### **7.4.1 Principal Investigator/Research Team**

The clinical research team will meet on a regular weekly basis when participants are being actively treated on the trial to discuss each participant. Decisions about dose level enrollment and dose escalation if applicable will be made based on the toxicity data from prior participants.

All data will be collected in a timely manner and reviewed by the principal investigator or a lead associate investigator. Events meeting requirements for expedited reporting as described in section [7.2.1](#) will be submitted within the appropriate timelines.

The principal investigator will review adverse event and response data on each participant to ensure safety and data accuracy. The principal investigator will personally conduct or supervise the investigation and provide appropriate delegation of responsibilities to other members of the research staff.

## **8 SPONSOR PROTOCOL/SAFETY REPORTING**

### **8.1 DEFINITIONS**

#### **8.1.1 Adverse Event**

Any untoward medical occurrence in a participant or clinical investigation subject administered a pharmaceutical product and which does not necessarily have a causal relationship with this treatment. An adverse event (AE) can therefore be any unfavorable and unintended sign (including an abnormal laboratory finding), symptom, or disease temporally associated with the use of a medicinal (investigational) product, whether or not related to the medicinal (investigational) product (ICH E6 (R2))

#### **8.1.2 Serious Adverse Event (SAE)**

An adverse event or suspected adverse reaction is considered serious if in the view of the investigator or the sponsor, it results in any of the following:

- Death,
- A life-threatening adverse event (see section [8.1.3](#))
- Inpatient hospitalization or prolongation of existing hospitalization
  - A hospitalization/admission that is pre-planned (i.e., elective or scheduled surgery arranged prior to the start of the study), a planned hospitalization for pre-existing

condition, or a procedure required by the protocol, without a serious deterioration in health, is not considered a serious adverse event.

- A hospitalization/admission that is solely driven by non-medical reasons (e.g., hospitalization for patient or subject convenience) is not considered a serious adverse event.
- Emergency room visits or stays in observation units that do not result in admission to the hospital would not be considered a serious adverse event. The reason for seeking medical care should be evaluated for meeting one of the other serious criteria.
- Persistent or significant incapacity or substantial disruption of the ability to conduct normal life functions
- A congenital anomaly/birth defect
- Important medical events that may not result in death, be life-threatening, or require hospitalization may be considered a serious adverse drug experience when, based upon appropriate medical judgment, they may jeopardize the patient or subject and may require medical or surgical intervention to prevent one of the outcomes listed in this definition.

#### 8.1.3 Life-threatening

An adverse event or suspected adverse reaction is considered "life-threatening" if, in the view of either the investigator or sponsor, its occurrence places the patient or subject at immediate risk of death. It does not include an adverse event or suspected adverse reaction that, had it occurred in a more severe form, might have caused death. (21CFR312.32)

#### 8.1.4 Severity

The severity of each Adverse Event will be assessed utilizing the CTCAE version 5.

#### 8.1.5 Relationship to Study Product

All AEs will have their relationship to study product assessed using the terms: related or not related.

- Related – There is a reasonable possibility that the study product caused the adverse event. Reasonable possibility means that there is evidence to suggest a causal relationship between the study product and the adverse event.
- Not Related – There is not a reasonable possibility that the administration of the study product caused the event.

#### 8.1.6 Adverse Events of Special Interest (AESI)

Neurological toxicity is considered an AESI and should be reported following SAE reporting procedures in Section **8.3** irrespective of temporal relationship to study drug administration and regardless of causality.

### **8.2 ASSESSMENT OF SAFETY EVENTS**

AE information collected will include event description, date of onset, assessment of severity and relationship to study product and alternate etiology (if not related to study product), date of resolution (or stabilization) of the event, seriousness and outcome. The assessment of severity and relationship to the study product will be done only by those with the training and authority to make

a diagnosis and listed on the Form FDA 1572 as the site principal investigator or sub-investigator. AEs occurring during the collection and reporting period will be documented appropriately regardless of relationship. AEs will be followed through resolution.

SAEs will be:

- Assessed for severity and relationship to study product and alternate etiology (if not related to study product) by a licensed study physician listed on the Form FDA 1572 as the site principal investigator or sub-investigator.
- Recorded on the appropriate SAE report form, the medical record and captured in the clinical database.
- Followed through resolution by a licensed study physician listed on the Form FDA 1572 as the site principal investigator or sub-investigator.

For timeframe of recording adverse events, please refer to Section **6.1**.

### **8.3 REPORTING OF SERIOUS ADVERSE EVENTS**

Any AE that meets protocol-defined serious criteria or meets the definition of Adverse Event of Special Interest that require expedited reporting must be submitted immediately (within 24 hours of awareness) to OSRO Safety using the CCR SAE report form. Any exceptions to the expedited reporting requirements are found in section **8.5**

All SAE reporting must include the elements described in section **8.2**. All serious adverse events recorded from the time of first investigational product administration to 30 days after last investigational product administration must be reported to the sponsor with the exception of any listed in Section **8.4**.

SAE reports will be submitted to the Center for Cancer Research (CCR) at: [[contact]](mailto:[contact]) and to the CCR PI and study coordinator. CCR SAE report form and instructions can be found at: <https://ccrod.cancer.gov/confluence/display/CCRCRO/Forms+and+Instructions>

Following the assessment of the SAE by OSRO, other supporting documentation of the event may be requested by the OSRO Safety and should be provided as soon as possible.

### **8.4 WAIVER OF EXPEDITED REPORTING TO CCR**

As death due to disease progression is part of the study objectives (PFS), and captured as an endpoint in this study, they will not be reported in expedited manner to the sponsor. However, if there is evidence suggesting a causal relationship between the study drug and the event, the event will be reported in an expedited manner according to Section **8.3**.

### **8.5 SAFETY REPORTING CRITERIA TO THE PHARMACEUTICAL COLLABORATORS**

Reporting will be per the collaborative agreement.

### **8.6 REPORTING PREGNANCY**

All required pregnancy reports/follow-up to OSRO will be submitted to: [[contact]](mailto:[contact]) and to the CCR PI and study coordinator. Forms and instructions can be found here: <https://ccrod.cancer.gov/confluence/display/CCRCRO/Forms+and+Instructions>

### 8.6.1 Maternal exposure

If a participant becomes pregnant during the course of the study, the study treatment should be discontinued immediately, and the pregnancy reported to the Sponsor no later than 24 hours of when the Investigator becomes aware of it. The Investigator should notify the Sponsor no later than 24 hours of when the outcome of the Pregnancy becomes known.

Pregnancy itself is not regarded as an SAE. However, congenital abnormalities or birth defects and spontaneous miscarriages that meet serious criteria (Section [8.1.2](#)) should be reported as SAEs.

The outcome of all pregnancies should be followed up and documented until 6 months after last dose of study drug.

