### 8.6.2 Paternal exposure

Male participants should refrain from fathering a child or donating sperm during the study and for 6 months after the last dose of KPT-8602 or Inqovi.

Pregnancy of the participant's partner is not considered to be an AE. However, the outcome of all pregnancies occurring from the date of the first dose until 6 months after the last dose should, if possible, be followed up and documented. Pregnant partners may be offered the opportunity to participate in an institutional pregnancy registry protocol (e.g., the NIH IRP pregnancy registry study) to provide data about the outcome of the pregnancy for safety reporting purposes.

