## **12 HUMAN SUBJECTS PROTECTIONS**

### **12.1 RATIONALE FOR PARTICIPANT SELECTION**

No participants will be excluded from participation based on gender, race or ethnicity. The study will be open to all participants who satisfy the inclusion criteria and provide an informed consent to the protocol.

Participants with active HIV, HCV, or HBV are excluded because study treatment can pose more risks for these participants.

Due to the unknown effects of KPT-8602 on the fetus and infants, and known teratogenicity of Inqovi, women of reproductive age will only be allowed to enroll if they commit to following a strict manner of contraception; Females who are breast-feeding will not be eligible for the trial. Men who are sexually active with women of childbearing age will also have to commit to strict contraceptive practices while on study.

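### Section 8.6.1, read literally, ends active follow-up of a participant's pregnancy 6 months after the last dose, before a term birth on the planned test schedule, so a birth defect can be missed

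*Combined protocol and SAP*

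**What the plan says.** Section 8.6.1 deals with pregnancy in a participant. It requires that "the study treatment should be discontinued immediately" and that the sponsor hear of the pregnancy within 24 hours. It then sets the length of follow-up: "The outcome of all pregnancies should be followed up and documented until 6 months after last dose of study drug".

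Two other sentences in 8.6.1 carry no end date. One concerns notification: "The Investigator should notify the Sponsor no later than 24 hours of when the outcome of the Pregnancy becomes known". The other makes reportable as serious adverse events (SAEs) the "congenital abnormalities or birth defects and spontaneous miscarriages that meet serious criteria". Section 8.1.2 lists "A congenital anomaly/birth defect" among the seriousness criteria.

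Section 8.6.2 deals with pregnancy in a participant's partner. What is to be followed, where possible, is "the outcome of all pregnancies occurring from the date of the first dose until 6 months after the last dose". Here the 6 months qualifies when the pregnancy occurs. No limit is put on how long each one is followed.

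Two general rules also bear on the point. Under Section 6.1, recording beyond 30 days after the last dose is confined to serious events related to the study investigational agent, with no end date. Section 8.3 requires reporting to the sponsor of SAEs recorded up to 30 days after the last investigational product.

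**The concern.** Treatment stops when the pregnancy is found, so the date of the last dose lies early in gestation. A clock of 6 months from that date runs out before a term delivery unless dosing continued well into the pregnancy. The outcome that matters most for a teratogenic drug, the condition of the infant at birth, then falls after active follow-up has closed.

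The plan itself gives the reason to want that outcome. Section 12.1 refers to the "known teratogenicity of Inqovi" and to unknown fetal effects of KPT-8602. Section 12.3.1 lists embryo-fetal toxicity as a risk. Read literally, the two halves of Section 8.6 also give a participant who took the drugs herself a shorter follow-up than a participant's partner, and no reason is offered.

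**Working it through.** The 6 months is a stated rule, not a derived figure, so there is nothing to reproduce. The check is calendar arithmetic.

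**Inputs from the documents**
- Follow-up ends 6 months after the last dose (8.6.1): 6 × 30.44 = 182.6 days = 26.1 weeks.
- Pregnancy tests fall on Day 1 of each cycle; from cycle 2 the window is 3 days early (3.5.2).
- The last planned KPT-8602 day in a cycle is Day 21 at the latest (3.1.2).
- Post-therapy phone calls are every 3 months for 24 months (3.4.1).

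**Assumptions, not in the documents**
- Term is 37 to 42 weeks' gestation. Gestation is counted from 2 weeks before conception, so term is (37 − 2) × 7 = 245 to (42 − 2) × 7 = 280 days after conception; 40 weeks is 266 days.
- A Day 1 test can miss a conception up to about 14 days old.

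**Longest lag on the planned schedule.** A conception just missed by a Day 1 test is followed by one more cycle of dosing, and the next test stops treatment. The lag from conception to last dose is then at most about 14 + 3 + 21 = 38 days. If a whole cycle is deferred (up to 28 days between cycles, 3.4.1), the next test is later, but no doses are given in the gap, so the last dose does not move.

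**Where follow-up ends.** Days after conception = lag + 182.6. Weeks' gestation = that figure / 7 + 2.

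| Lag, conception to last dose (days) | Follow-up ends (weeks' gestation) | Days short of 37 weeks | Days short of 40 weeks |
|---|---|---|---|
| 0 | 28.1 | 62 | 83 |
| 14 | 30.1 | 48 | 69 |
| 28 | 32.1 | 34 | 55 |
| 38 | 33.5 | 24 | 45 |
| 56 | 36.1 | 6 | 27 |
| 70 | 38.1 | reached | 13 |
| 84 | 40.1 | reached | reached |

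**Lag needed to reach birth.** 245 − 182.6 = 62 days for a 37-week birth, 266 − 182.6 = 83 days for 40 weeks, and 280 − 182.6 = 97 days for 42 weeks. The planned schedule gives at most about 38. Missed doses extend dosing by a day each (3.2.1), but 62 − 38 = 24 such days would be needed to reach even 37 weeks.

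**Conception after the last dose.** Follow-up ends at (182.6 − s) / 7 + 2 weeks' gestation, where s is days from last dose to conception. For s = 30, 90 and 183 this is about 23.8, 15.2 and 1.9 weeks. A 40-week birth would fall (s + 266) / 30.44 = 9.7, 11.7 and 14.8 months after the last dose.

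**Do other provisions fill the gap?** For lags of 0 to 38 days, a 40-week birth falls 266 / 30.44 = 8.7 down to (266 − 38) / 30.44 = 7.5 months after the last dose, ahead of the call due at about 9 months. Appendix I lists survival, adverse events, progression and secondary AML for those calls. It has no pregnancy-outcome item.

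**The case against.** The strongest reply is that the plan does not stop listening at 6 months. The outcome-notification and birth-defect sentences in 8.6.1 are open-ended, 6.1 keeps related serious events in scope indefinitely, and adverse events are collected at the 3-monthly calls. A term birth could well come up at one of them. This stands in part: a defect reported spontaneously after 6 months could still be captured. But these provisions act on an outcome that has become known, and after 6 months nobody is required to ask. Section 8.3 limits sponsor reporting to 30 days. The wording of 6.1 (study investigational agent) may not extend to Inqovi, which 3.2.2 describes as standard of care and 14.2.1 as commercially purchased.

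A second reply is that the sentence is loose drafting and was meant as in 8.6.2. That is plausible, and it is a reason to reconcile the two. It does not remove the problem for staff who follow 8.6.1 as written. Section 8.6 also points to sponsor forms and instructions that are not in the documents and may set a duration; this cannot be checked.

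A third is that cases will be rare. Median age at MDS diagnosis is about 75 (1.2.1), pregnancy is excluded (2.1.2.7), contraception is required (2.1.1.6), and the accrual ceiling is 80 (10.2). This stands and limits the practical weight.

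A reader might go further and infer that every term birth from an on-study conception falls outside follow-up, so that birth defects will be lost. The documents do not support that. If dosing ran on for about 9 to 14 weeks after conception, for example after missed tests, the window would reach a birth at 37 to 42 weeks. Anomalies found prenatally, at miscarriage or at preterm birth within the window would be captured, and later ones could be reported spontaneously.

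**Conclusion.** The point holds in a limited form. Under the literal wording of 8.6.1, active outcome follow-up closes at about 33.5 weeks' gestation at the latest for a conception detected on the planned tests. That is 24 days before 37 weeks and 45 days before 40 weeks. It closes earlier for shorter lags and for conceptions after the last dose. A birth defect can therefore be missed; it is not certain to be.

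The result rests on term at 37 to 42 weeks, a test that misses conceptions up to about 14 days old, and tests done as scheduled. Sections 8.6.1 and 8.6.2 use the same 6 months for different purposes, and 6.1 and 8.3 do not clearly back up either. This is a safety-reporting matter with few expected cases. It leaves the efficacy endpoints and sample size untouched.

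**What to change.** Reconcile 8.6.1 with 8.6.2 so that the 6 months defines which pregnancies are covered and each covered pregnancy is followed to its outcome, whether delivery, loss or termination. State whether the rule runs from the last dose of KPT-8602, Inqovi or either; 8.6.2 names both drugs in its advice on fathering a child, while 8.6.1 says only study drug.

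Check 6.1 and 8.3 against the new sentence, so that a birth defect found more than 30 days after the last dose is clearly recordable and reportable, including one attributed to Inqovi. Adding a pregnancy-outcome item to the post-therapy list in Appendix I would make the existing calls ask the question.

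The cost is one sentence in 8.6.1, plus any matching edits in 6.1, 8.3 and Appendix I. The phone contacts and pregnancy report forms already exist, and no new visits are needed.

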### 8.6.2 Paternal exposure

Male participants should refrain from fathering a child or donating sperm during the study and for 6 months after the last dose of KPT-8602 or Inqovi.

Pregnancy of the participant's partner is not considered to be an AE. However, the outcome of all pregnancies occurring from the date of the first dose until 6 months after the last dose should, if possible, be followed up and documented. Pregnant partners may be offered the opportunity to participate in an institutional pregnancy registry protocol (e.g., the NIH IRP pregnancy registry study) to provide data about the outcome of the pregnancy for safety reporting purposes.

## 8.7 REGULATORY REPORTING FOR STUDIES CONDUCTED UNDER CCR-SPONSORED IND

Following notification from the investigator, CCR, the IND sponsor, will report any suspected adverse reaction that is both serious and unexpected in expedited manner to the FDA in accordance to 21 CFR 31.2.32. CCR will report an AE as a suspected adverse reaction only if there is evidence to suggest a causal relationship between the study product and the adverse event. CCR will notify FDA and all participating investigators (i.e., all investigators to whom the sponsor is providing drug under its INDs or under any investigator's IND) in an IND safety report of potential serious risks from clinical trials or any other source, as soon as possible, in accordance to 21 CFR Part 312.32.

All serious events will be reported to the FDA at least annually in a summary format.

## 8.8 SPONSOR PROTOCOL DEVIATION REPORTING

Protocol deviation is defined as any noncompliance with the clinical trial protocol, Manual of Operational Procedures (MOP) and other Sponsor approved study related documents, GCP, or protocol-specific procedural requirements on the part of the participant, the Investigator, or the study site staff inclusive of site personnel performing procedures or providing services in support of the clinical trial.

It is the responsibility of the study Staff to document any protocol deviation identified by the Staff or the site Monitor in the CCR Protocol Deviation Tracking System (PDTs) online application. The entries into the PDTs online application should be timely, complete, and maintained per CCR PDTs user requirements.

In addition, any deviation to the protocol should be documented in the participant's source records and reported to the reviewing IRB per their guidelines. OSRO required protocol deviation reporting is consistent with E6(R2) GCP: Integrated Addendum to ICH E6(R1): 4.5 Compliance with Protocol; 5.18.3 (a), and 5.20 Noncompliance; and ICH E3 16.2.2 Protocol deviations.

## **9 CLINICAL MONITORING**

Clinical site monitoring is conducted to ensure:

- that the rights of the participants are protected,
- that the study is implemented per the approved protocol, Good Clinical Practice and standard operating procedures; and
- that the quality and integrity of study data and data collection methods are maintained.

Monitoring for this study will be performed by NCI CCR Office of Sponsor and Regulatory Oversight (OSRO) Monitoring and Regulatory Oversight Support (SROS) Services contractor. Clinical site monitoring activities will be based on OSRO standards, FDA Guidance E6(R2) Good Clinical Practice: Integrated Addendum to ICH E6(R1) March 2018, and applicable regulatory requirements.

Details of clinical site monitoring will be documented in a Clinical Monitoring Plan (CMP) developed by OSRO. CMPs will be protocol-specific, risk-based and tailored to address human subject protections and integrity of the study data. OSRO will determine the intensity and frequency of monitoring will be based on several factors, including study type, phase, risk, complexity, expected enrollment rate, and any unique attributes of the study and the site. The Sponsor will conduct a periodic review of the CMP to confirm the plan's continued appropriateness. A change to the protocol, significant or pervasive non-compliance with GCP, or the protocol may trigger CMP updates.

OSRO-SROS Monitoring visits and related activities will be conducted throughout the life cycle of each protocol. The first activity is before the study starts, to conduct a Site Assessment Visit (SAV) (as warranted), followed by a Site Initiation Visit (SIV), Interim Monitoring Visit(s) (IMVs), and a study Close-Out Visit (COV).

Some monitoring activities may be performed remotely, while others will take place at the study site(s). Monitoring visit reports will describe visit activities, observations, findings of protocol non-adherence and associated action items or follow-up required for resolution of findings. Monitoring reports will be distributed to the study PI, NCI CCR QA, coordinating center (if applicable) and the OSRO regulatory file.

The site Monitor will inform the study team of any deviations observed during monitoring visits. If unresolved, the Monitor will request that the site Staff enter the deviations in the CCR Protocol Deviation Tracking System (PDTs) for deviation reporting to the Sponsor and as applicable per institutional and IRB guidance.

